8.7.2.2. Measures of association

For comparative analyses of general safety events, Cox models or Poisson regression will be used to estimate RRs and 95% CIs within the matched cohorts. For pregnancy outcomes, hazard ratios and 95% CIs will be estimated using Fine-Gray subdistribution proportional hazards models (using gestational age as the time scale) to account for competing risks of other end-of-pregnancy events (e.g., termination, stillbirth) (Fine JP and Gray RJ, 1999).

For comparative analysis of small size for gestational age and major congenital malformations, modified Poisson regression (Zou, 2004) will be used to estimate prevalence ratios and 95% CIs within the matched cohorts.

For the dose 1 comparative risk estimation for general safety events and pregnancy outcomes, when a second dose of vaccine is administered before the risk interval following dose 1 is complete, the risk interval will be truncated at the time of dose 2, and FU after dose 2 will be excluded from the dose 1 risk estimation. In this situation, for the dose 2 comparative risk estimation, the risk interval will start on the date of the second vaccine dose and will extend for the duration of the risk interval for dose 2.

Similarly, for dose 2 comparative risk estimation for general safety events and pregnancy outcomes, when a third dose of vaccine is administered before the risk interval following dose 2 is complete, the risk interval will be truncated at the time of dose 3, and FU after dose 3 will be excluded from the dose 2 estimation. In this situation, for the dose 3 comparative risk estimation, the risk interval will start on the date of the third vaccine dose and will extend for the duration of the risk interval for dose 3.

For comparative analysis of outcomes identified separately in dose 1, dose 2, and dose 3 cohorts, comparative risks will be estimated separately by dose number. If comparative risk estimates are similar for dose 1, dose 2, and dose 3, then data from the dose 1 exposed/dose 1 unexposed cohorts, the dose 2 exposed/dose 2 unexposed cohorts, and the dose 3 exposed/dose 3 unexposed cohorts will be combined to obtain comparative risk estimates associated with at least 1 dose of the vaccine.

Because each dose of vaccine within the same individual will be considered a separate observation when combined in analyses and because some individuals may contribute to both the exposed and unexposed cohorts, the correlation between dose 1, dose 2, and dose 3 will

PFIZER CONFIDENTIAL CT24-WI-GL02-RF02 3.0 Non-Interventional Study Protocol Template For Secondary Data Collection Study 20-May-2021 Page 91 of 120 be accounted for when estimating the variance, using appropriate statistical methods to be detailed in the SAP.

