Pfizer is conducting a phase 1/2/3, randomized, placebo-controlled, observer-blind, dose-finding, vaccine candidate-selection, and efficacy studies among healthy individuals aged 18 years and above (phase 1) and individuals aged 12 years and above (phases 2/3) (NCT04368728). Initial efficacy and safety results from this ongoing multinational trial were reported in December 2020 for 43,448 individuals aged 16 years or older who received injections (21,720 with BNT162b2 and 21,728 with placebo) and showed that a 2-dose regimen was 95% effective in preventing COVID-19 (Polack et al., 2020). Safety was assessed in 37,706 participants with a median of at least 2 months of data available after the second dose, with most adverse events (AEs) being transient reactogenicity events; the most commonly reported AEs were pain at the injection site (84.1%), fatigue (62.9%), headache (55.1%), muscle pain (38.3%), chills (31.9%), joint pain (23.6%), and fever (14.2%) (Pfizer and BioNTech, 2020). The incidence of serious AEs was similar across the vaccine (0.6%) and placebo (0.5%) groups (Polack et al., 2020). An imbalance was noted in the occurrence of Bell's palsy, with 4 cases in the vaccine group and no cases in the placebo group, but the frequency was not in excess of that expected among the general population (Pfizer and BioNTech, 2020).

Efficacy and safety results for 2,260 children aged 12 to 15 years were initially reported in May 2021 (1,131 who received BNT162b2 and 1,129 who received placebo) (Frenck et al., 2021). No COVID-19 cases with onset of 7 or more days after dose 2 occurred among recipients of BNT162b2, and 18 cases occurred among recipients of placebo, for an observed vaccine efficacy of 100% (95% confidence interval [CI], 78.1%-100%). Adverse events were mainly transient, mild to moderate reactogenicity events such as injection site pain (in 79%-86% of study participants), fatigue (in 60%-66% of participants), and headache (in 55%-65% of participants). No vaccine-related serious AEs occurred, and severe AEs were very rare (in 0.2% of BNT162b2 recipients).

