Respiratory	Acute respiratory distress syndrome	1-28
	Vaccine-associated enhanced respiratory disease	1-365
Other system	Anaphylaxis	0-1
	Appendicitis	1-42
	Kawasaki disease	1-42
	Multisystem inflammatory syndrome	1-42

COVID-19 = coronavirus disease 2019.

a. Time interval following vaccination when individuals will be followed for safety events of interest. Day 0 refers to the day of vaccination.

b. Sensitivity analysis will assess alternative risk interval definitions of 1-7 and 1-14 days.

The following pregnancy safety outcomes will be assessed in pregnant women or their infants:

- Spontaneous abortion: spontaneous pregnancy loss before 20 completed weeks gestation, identified using diagnosis codes
- Stillbirth: fetal deaths at or after 20 completed weeks gestation, identified using diagnosis codes

PFIZER CONFIDENTIAL

CT24-WI-GL02-RF02 3.0 Non-Interventional Study Protocol Template For Secondary Data Collection Study 20-May-2021 Page 69 of 120

- Preterm birth: live birth before 37 completed weeks gestation, identified using diagnosis codes
- Major congenital malformations: major congenital malformations will be identified in live-born infants using code lists from the National Birth Defects Prevention Network (NBDPN, 2021a), which defines a major defect as a congenital abnormality that requires medical or surgical treatment, has a serious adverse effect on health and development, or has significant cosmetic impact (NBDPN, 2021b)
- Small size for gestational age: less than 10th percentile of weight for gestational age, identified using diagnosis codes for small size for gestational age

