8.7.2. Measures of disease frequency and association

All eligible individuals in each study cohort will be included in analysis of disease frequency and measures of association. However, in analysis of some safety events, individuals who have experienced the outcome in the recent past will be excluded from the analysis. This will be done to distinguish between FU care for events that have happened in the past from incident events occurring during FU. The washout periods for defining incident events will depend on the outcome and will be specified in the SAP.

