8.7.2.3. Methods for addressing confounding

8.7.2.3.1. General population, immunocompromised individuals, and individuals with a history of COVID-19

Analysis of nonpregnant populations will use matching on age, sex, state (if feasible, or broader geographic region if not feasible), and time–specific propensity scores within the data from each data research partner to account for confounding. The propensity score is the predicted probability of an individual being in the exposed cohort rather than in the corresponding unexposed cohort, given a set of observed covariates. Additionally, analysis of third doses received more than 2 months after the second dose will also match on time since receipt of the second dose.

8.7.2.3.1.1. Analysis of general safety events following primary series

Among the general population, immunocompromised individuals, and individuals with a history of COVID-19, the risk of general safety events will be compared among individuals who have received at least the first dose in a primary series of Pfizer-BioNTech original monovalent COVID-19 Vaccine versus those among individuals who have not received any COVID-19 vaccine during a concurrent time. In individuals aged 6 months through 4 years, these analyses will include doses 1, 2, and 3. Details for handling the timing between individual doses in this age group will be described in the SAP. In individuals aged 5 years and older, these analyses will include dose 1 and dose 2, as well as dose 3 if a third dose is received within 2 months of the second dose.

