- c. Within each data research partner, the distribution of propensity scores in each dose cohort in each time interval will be plotted to evaluate the comparability of the 2 exposure groups. Greater overlap of the propensity score distributions will indicate greater exchangeability.
- d. After the comparability of the treatment groups is confirmed, unexposed individuals will be matched on propensity scores to exposed individuals (in a ratio of at least 1:1) within each data research partner. The matching will be done separately for the dose 1 exposed cohort, for the dose 2 exposed cohort, and for the dose 3 exposed cohort and will be done by age and state (or geographic region) within each time interval.
- e. The matching procedure within each dose cohort will be executed chronologically from 1 time interval to the next time interval. An individual may only be selected once for the dose 1 unexposed cohort, once for the dose 2 unexposed cohort, and once for the dose 3 unexposed cohort. Individuals who match as an unvaccinated index date in one time interval will not be considered for the same unvaccinated cohort (i.e., dose 1 unexposed cohort, dose 2 unexposed cohort, or dose 3 unexposed cohort) in future time intervals. However, if an individual becomes vaccinated after being selected as an unexposed match, they may be eligible for the dose 1, dose 2, and/or dose 3 exposed cohorts.
- f. The matched exposed and unexposed individuals from each time interval will be combined into the overall matched analytic cohorts.

Further details on the matching process and estimation of propensity scores will be described in the SAP.

8.7.2.3.1.2. Analysis of general safety events following third doses received more than 2 months after the second dose in individuals aged 5 years and older

In individuals aged 5 years and older who have received 2 doses in a primary series of Pfizer-BioNTech original monovalent COVID-19 Vaccine, the risk of general safety events will be compared in individuals who have received a third dose (either as an additional dose within a

PFIZER CONFIDENTIAL CT24-WI-GL02-RF02 3.0 Non-Interventional Study Protocol Template For Secondary Data Collection Study 20-May-2021 Page 93 of 120 primary series or as a booster dose) more than 2 months after the second dose, versus that among individuals who have not received a third dose of any COVID-19 Vaccine during a concurrent time period.

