A study design-related limitation is that any uncertainty regarding risk periods will lead to misclassification and attenuation of risk estimates. Sensitivity analyses with alternative risk intervals will be considered for outcomes for which the risk interval is not well characterized.

A limitation of the cohort design with concurrent unexposed comparators is the potential for residual or unmeasured confounding because it is unlikely that the data sources will have information on all potential confounders. To address potential confounding and potential misclassification of unexposed status, the SCRI, which automatically adjusts for time-invariant confounders, will be used as a secondary approach where feasible. However, the SCRI is not well suited to study outcomes with gradual onset, long risk intervals, or risk periods that are not well characterized.

A limitation specific to the cohort design with concurrent unexposed comparators is that unvaccinated individuals may become exposed to COVID-19 vaccine at any time during the study; if this situation occurs frequently, the amount of unexposed person-time in the unexposed comparator group will be reduced substantially, which will limit the precision of comparative risk estimates and could potentially lead to substantial imbalances in seasonality between exposed individuals and unexposed individuals, particularly for outcomes with long risk intervals. In primary series analyses, forming separate exposed cohorts by dose number and matching unexposed to exposed at the time of each vaccine will minimize the loss of unexposed person-time due to receipt of vaccine in these individuals between the first and second doses. Additionally, the sensitivity analyses with the historical unexposed comparator cohort for pregnancy and birth outcomes and the SCRI design will not be subject to this limitation. However, it is anticipated that even with separate matching of doses that FU time will be substantially longer in analyses of vaccine-associated enhanced respiratory disease in individuals in the vaccinated cohorts than in the unvaccinated comparator cohorts, since the risk interval is 365 days long. Further, the SCRI design and historical unexposed comparator cohort design are not feasible to be used to study this outcome.

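### For vaccine-associated enhanced respiratory disease, the planned incidence RR mixes prevention of COVID-19 with severity once infected, so an RR at or below 1 cannot exclude enhancement

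*Protocol*

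**What the plan says.** Table 8 (Section 8.3.2.1) lists "Vaccine-associated enhanced respiratory disease" among the general safety events with a risk window of days 1-365. It is one of a few outcomes that the study adds to those taken from the federal surveillance systems.

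The protocol fixes the comparison for all general safety events:

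- **Estimator (8.7.2.2):** "Cox models or Poisson regression will be used to estimate RRs and 95% CIs within the matched cohorts".
- **Denominator (8.7.2):** "All eligible individuals in each study cohort will be included in analysis of disease frequency and measures of association". The only exclusion named there is for a recent prior occurrence of the outcome.
- **Primary-series comparator (8.7.2.3.1.1):** vaccinees "versus those among individuals who have not received any COVID-19 vaccine during a concurrent time".
- **Late third-dose comparator (8.7.2.3.1.2):** third-dose recipients "versus that among individuals who have not received a third dose of any COVID-19 Vaccine during a concurrent time period". Both groups have already had two doses.

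For this outcome in particular, Section 8.7.1 adds only a description of follow-up length. Section 8.9 warns that follow-up will be longer in vaccinees, "since the risk interval is 365 days long", and then says: "Further, the SCRI design and historical unexposed comparator cohort design are not feasible to be used to study this outcome". The case algorithm is left to the SAP (8.3.2.2).

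**The concern.** As its name says, the outcome is disease made worse by vaccination. It can arise only in someone who becomes infected, so the quantity of interest is severity among infected vaccinees relative to severity among comparable infected people without the dose. The planned RR has everyone in its denominator and therefore also carries the vaccine's effect on getting COVID-19 at all. A vaccine that prevents most cases and worsens the remainder can produce an RR below 1.

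Nothing else in the protocol separates the two effects. No comparison is restricted to infection after the index date. The history-of-COVID-19 subcohort (8.3.3.2) does not serve, because it is defined by past COVID-19. The self-controlled and historical designs are ruled out for this outcome, and the masking is not among the limitations in 8.9. The study could therefore report an RR below 1 for an outcome chosen to detect harm, with no warning that this RR does not address enhancement.

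**Working it through.** **Inputs from the protocol**

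- VE against COVID-19, age 16 and older, two-dose regimen, results reported December 2020: 95% (Section 6). Case counts are not given, so this cannot be re-derived.
- VE against COVID-19, ages 5-11: 90.7%, 95% CI 67.4-98.3% (Section 6), from 3 cases in 1,517 vaccinees and 16 in 751 placebo recipients. Check: 1 - (3/1517)/(16/751) = 1 - 0.00198/0.02130 = 0.907. It reproduces.
- Table 9 gives no size or precision figure for this outcome, so there is no planned value to compare with.

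**Assumed, not in the protocol:** VE of 50% and 30%, to represent waned protection within the 365-day window.

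**Formula**

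Risk of severe COVID-19 = risk of COVID-19 x risk of severe disease given COVID-19. Taking the ratio of vaccinated to comparator:

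RR = (1 - VE) x S

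Here S is the ratio of severe-disease risk per COVID-19 case. S = 1 means no enhancement and S = 2 means that severity doubles. The RR reaches 1 only when S = 1/(1 - VE).

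**Results**

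| VE | Source | RR if S = 1 | RR if S = 2 | S at which RR = 1 |
|---|---|---|---|---|
| 95% | Section 6, age 16 and older | 0.05 | 0.05 x 2 = 0.10 | 1/0.05 = 20 |
| 90.7% | Section 6, ages 5-11 | 0.093 | 0.093 x 2 = 0.19 | 1/0.093 = 10.8 |
| 67.4% | lower CI limit, ages 5-11 | 0.326 | 0.326 x 2 = 0.65 | 1/0.326 = 3.1 |
| 50% | assumed | 0.50 | 0.50 x 2 = 1.0 | 2.0 |
| 30% | assumed | 0.70 | 0.70 x 2 = 1.4 | 1.4 |

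In every row the RR is smaller than S. With the protocol's own efficacy figures a real doubling appears as a protective RR. At 50% it appears as no effect, and at 30% as a raised RR that still understates the doubling.

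**Unrecorded vaccination.** Sections 8.1 and 8.3.1 warn that some people classed as unexposed will have been vaccinated. If a fraction m of them was (m is an assumption), the observed RR is RR/[(1 - m) + m x RR]. For S = 2 and m = 0.4:

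- VE 95%: 0.10/(0.6 + 0.04) = 0.16
- VE 90.7%: 0.186/(0.6 + 0.074) = 0.28

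This moves the RR toward 1 but does not remove the masking.

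**The case against.** **The algorithm is in the SAP, and Section 8.7 lets the SAP modify the plan.** Both are true, and the absence of an algorithm here is no fault. But a case definition sets the numerator, while the denominator and estimator are set in 8.7.2 and 8.7.2.2. If the algorithm requires COVID-19, the formula above applies. If it also counts other respiratory disease, the RR is diluted but severity is still not isolated. If it requires vaccination, unexposed cases in the primary-series comparison are zero by definition.

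**The 95% figure is stretched.** This stands in good part. It is an early result for a completed two-dose regimen. It does not describe the dose 1 cohort, whose follow-up stops at dose 2, nor necessarily a full 365-day window with exposures up to 18 April 2023. It is efficacy against COVID-19, so S must be read per COVID-19 case and not per infection. The 0.10 and the 20-fold break-even are one end of a range.

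**The net effect is a legitimate target.** This also stands. The objectives ask for the RR of events after vaccination, and the protocol sets no rule by which an RR below 1 would exclude enhancement. The incidence RR should stay, with its meaning stated.

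**Conditioning on infection has its own bias.** It selects on an event after exposure that the vaccine itself affects, and that may be recorded unequally. If mild cases go unrecorded more often in the unvaccinated, their apparent severity rises and enhancement is masked again. A reader might infer that the infection-conditional contrast should replace the incidence RR as the main measure. Given this bias, the documents do not support that.

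**Conclusion.** The point holds as a limit on interpretation. For this outcome, the planned RR is a net effect on severe COVID-19, and a value at or below 1 cannot exclude enhanced disease. A doubling of severity would give an RR between 0.10 and 0.65 at the efficacies taken from Section 6, and 1.0 to 1.4 at assumed efficacies of 50% to 30%. This rests on the product formula, which is exact for an algorithm that counts severe COVID-19, and on a constant VE over the window.

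Two stronger readings are tempting but unsupported. One is that the RR will look protective whenever breakthrough disease is worsened. That is so only while S is below 1/(1 - VE), and at 50% or 30% efficacy a doubling is not protective. The other is that the comparison is always with unvaccinated people. The late third-dose analysis uses two-dose recipients. The same product applies there, with the third dose's incremental protection in place of VE, but the protocol gives no figure for it and the sizes above do not carry over.

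The other 24 events in Table 8, including myocarditis/pericarditis, are outside this point. It is an inexpensive improvement that changes what may be concluded about one outcome.

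**What to change.** 1. Keep the incidence RR as planned.
2. State in 8.7.2.2 and 8.9 that, for this outcome, the RR measures the net effect on severe COVID-19, combines prevention with severity, and cannot exclude enhanced disease.
3. Add a supplementary analysis, not the main one. Among matched-cohort members with a recorded COVID-19 diagnosis during follow-up, compare exposed with unexposed on the risk of meeting the severe-disease algorithm within a fixed period, for example 30 days, after that diagnosis. Adjust for calendar month of infection, age and comorbidity, because restricting to the infected breaks the matching. Within the exposed, describe results by time since dose.
4. Report beside it that the analysis conditions on a recorded infection after exposure, that recording may differ by vaccination status, and that the resulting bias can go either way.

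The cost is a short text change and one further analysis on data already held. The supplementary result will need cautious reading for the reason in item 4.

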8.7.2.3. Methods for addressing confounding

8.7.2.3.1. General population, immunocompromised individuals, and individuals with a history of COVID-19

Analysis of nonpregnant populations will use matching on age, sex, state (if feasible, or broader geographic region if not feasible), and time–specific propensity scores within the data from each data research partner to account for confounding. The propensity score is the predicted probability of an individual being in the exposed cohort rather than in the corresponding unexposed cohort, given a set of observed covariates. Additionally, analysis of third doses received more than 2 months after the second dose will also match on time since receipt of the second dose.

8.7.2.3.1.1. Analysis of general safety events following primary series

Among the general population, immunocompromised individuals, and individuals with a history of COVID-19, the risk of general safety events will be compared among individuals who have received at least the first dose in a primary series of Pfizer-BioNTech original monovalent COVID-19 Vaccine versus those among individuals who have not received any COVID-19 vaccine during a concurrent time. In individuals aged 6 months through 4 years, these analyses will include doses 1, 2, and 3. Details for handling the timing between individual doses in this age group will be described in the SAP. In individuals aged 5 years and older, these analyses will include dose 1 and dose 2, as well as dose 3 if a third dose is received within 2 months of the second dose.

Estimation of propensity scores will be performed for the dose 1, 2, and 3 (if applicable) cohorts combined. However, matching of exposed to unexposed individuals will be done separately for the dose 1 exposed cohort, the dose 2 exposed cohort, and the dose 3 exposed cohort within narrow time periods to account for changing predictors of vaccination over time, seasonality of circulating infections, and changes in healthcare utilization over time. Matching will occur by age and state (if feasible, or broader geographic region if not feasible) within each time period and dose number. The matching and propensity score estimation process will be done first for the general population and then will be repeated separately for immunocompromised individuals and for individuals with a history of COVID-19. Propensity score estimation will be conducted within each data research partner. The steps for propensity score modeling and matching are as follows.

a. Within each data research partner, the study period will be divided into 1-month intervals of calendar time ("time intervals"). All individuals who received a vaccine dose— whether dose 1, dose 2, or dose 3—during the considered month would contribute vaccinated index dates during the time interval; if an individual received more than 1 dose during a calendar month, all eligible index dates will be included as independent observations in the propensity score model. All individuals with at least 1 unexposed

PFIZER CONFIDENTIAL

CT24-WI-GL02-RF02 3.0 Non-Interventional Study Protocol Template For Secondary Data Collection Study 20-May-2021 Page 92 of 120 person-day in the time interval will have an unvaccinated index date randomly assigned during all unexposed person-time within the time interval. In this context, "unexposed person-day" refers to a day in which the individual has no record of COVID-19 vaccine on or before that day.

- b. Within each time interval, the propensity to be vaccinated will be estimated among all individuals with index dates within the time interval using logistic regression. The dependent variable for the logistic regression model will be vaccination status, and the independent variables will be baseline covariates (i.e., individual characteristics as described in Section 8.3.3). The model will combine dose 1, dose 2, and dose 3 index dates, which assumes that the factors influencing an individual's likelihood of being vaccinated does not change between dose 1, dose 2, and dose 3.
- c. Within each data research partner, the distribution of propensity scores in each dose cohort in each time interval will be plotted to evaluate the comparability of the 2 exposure groups. Greater overlap of the propensity score distributions will indicate greater exchangeability.
- d. After the comparability of the treatment groups is confirmed, unexposed individuals will be matched on propensity scores to exposed individuals (in a ratio of at least 1:1) within each data research partner. The matching will be done separately for the dose 1 exposed cohort, for the dose 2 exposed cohort, and for the dose 3 exposed cohort and will be done by age and state (or geographic region) within each time interval.
- e. The matching procedure within each dose cohort will be executed chronologically from 1 time interval to the next time interval. An individual may only be selected once for the dose 1 unexposed cohort, once for the dose 2 unexposed cohort, and once for the dose 3 unexposed cohort. Individuals who match as an unvaccinated index date in one time interval will not be considered for the same unvaccinated cohort (i.e., dose 1 unexposed cohort, dose 2 unexposed cohort, or dose 3 unexposed cohort) in future time intervals. However, if an individual becomes vaccinated after being selected as an unexposed match, they may be eligible for the dose 1, dose 2, and/or dose 3 exposed cohorts.
- f. The matched exposed and unexposed individuals from each time interval will be combined into the overall matched analytic cohorts.

Further details on the matching process and estimation of propensity scores will be described in the SAP.

8.7.2.3.1.2. Analysis of general safety events following third doses received more than 2 months after the second dose in individuals aged 5 years and older

In individuals aged 5 years and older who have received 2 doses in a primary series of Pfizer-BioNTech original monovalent COVID-19 Vaccine, the risk of general safety events will be compared in individuals who have received a third dose (either as an additional dose within a

PFIZER CONFIDENTIAL CT24-WI-GL02-RF02 3.0 Non-Interventional Study Protocol Template For Secondary Data Collection Study 20-May-2021 Page 93 of 120 primary series or as a booster dose) more than 2 months after the second dose, versus that among individuals who have not received a third dose of any COVID-19 Vaccine during a concurrent time period.

Estimation of propensity scores and matching will be performed for the dose 3 exposed cohort within narrow time periods to account for changing predictors of receipt of third doses of the vaccine over time and the seasonality of circulating infections. Matching will occur within each time period by age, sex, state (if feasible, or broader geographic region if not feasible), and time since dose 2 receipt. Propensity score estimation will be conducted following similar steps as for the primary series analysis (as described in Section 8.7.2.3.1.1). The matching and propensity score estimation process will be conducted first for the general population and then will be repeated separately for individuals who are immunocompromised and individuals with a history of COVID-19. Further details on the matching process and estimation of propensity scores will be described in the SAP.

